## 1.3 RATIONALE FOR THE STUDY OF LEAP SIBLINGS POPULATION: ASSESSING RISK FOR ALLERGIC SENSITIZATION

## 1.3.1 Anecdotal Observations from LEAP Families

During the LEAP Study, from discussions with families at the time of scheduled visits and from observations made during study-related phone calls, it became apparent that that siblings, especially younger ones, of LEAP participants born during LEAP may have been disproportionately affected with suspected peanut allergy. The initial analysis suggested that 13 siblings of 319 LEAP consumers may have developed peanut allergy as compared to none of the siblings born to 320 LEAP avoiders. This analysis was based on allergic symptoms after ingestion volunteered by parents and not by systematic questioning or formal allergy testing.

This finding could have reflected either a real difference in the prevalence of peanut allergy in the two groups or reporting bias on the part of parents in households where peanut consumption - and opportunity for exposure - was high. However, it raised the concern that intentional peanut consumption as specified for consuming children in the LEAP study could increase the risk of peanut allergy among siblings in the same household. This concern was discussed by the LEAP Study Management Team and independent ethical advice was sought.

## 1.3.2 Questionnaires to LEAP Families

To further investigate the anecdotal observations, local Ethics Committee approval for issuing a questionnaire (the 'LEAP and LEAP-On Sibling Peanut Allergy Questionnaire') was obtained in October 2013 through amendments to the LEAP Study (04/Q0403/13) and the LEAP-On Study (10/H0711/77). All LEAP participant families were then informed of the background to and need for completion of the LEAP and LEAP-On Sibling Peanut Allergy Questionnaire. Out of 640 families, 619 (97%) were contacted and of these, 600 (94%) provided informed consent and completed the questionnaire. Nineteen declined informed consent. 523 families had at least one more child in addition to the LEAP participant while 77 families did not have a LEAP sibling. In total, these consented families provided information for 746 siblings.

The LEAP and LEAP-On Sibling Peanut Allergy Questionnaire revealed a questionnairebased diagnosis of peanut allergy of 4.2% in younger siblings of the LEAP avoidance group participants and 9.2% in younger siblings of the LEAP consumption group participants (p-value of difference in proportions is 0.057 using a one-tailed Wald analysis). These findings therefore supported the original observation that early peanut introduction in high-risk children may have led to an increase in the rates of peanut allergy in the younger siblings of children who consumed peanut on the LEAP Study as compared to the younger siblings of LEAP participants who avoided peanut. However, similar to the anecdotal observations from LEAP families, these questionnaire-based findings may also have arisen due to ascertainment bias because the siblings of LEAP peanut avoiders are less likely to have been exposed to peanut and therefore have had less opportunity to manifest symptoms of peanut allergy. An additional source of uncertainty arises from the 78 younger siblings (56 in the avoidance group and 22 in the consumption group) for whom the questionnaire result was a 'don't know' outcome due to the fact that the sibling may never have eaten peanut or ever undergone peanut allergy testing.

## 1.3.3 Plans for Current Study of Siblings

The LEAP Siblings cohort in the current study therefore aims to further investigate the findings of the LEAP and LEAP-On Sibling Peanut Allergy Questionnaire using a more rigorous scientific methodology to exclude the possibility of ascertainment bias. The findings will serve as an important safety evaluation. Study of this cohort will also provide an opportunity to improve our understanding of how early introduction of peanuts promotes the development of tolerance, and will estimate the prevalence of peanut allergy in siblings of LEAP participants.

#### 1.4 RATIONALE FOR GENETIC STUDIES IN LEAP PARTICIPANTS AND FAMILIES, INCLUDING PARENTS

There are many risk factors associated with the development of food allergy (FA), including atopic family history, male sex (at least in childhood), ethnicity, atopic dermatitis (AD), and related genetic polymorphisms. Although genetic factors are clearly important in the development of food allergy, the increase in prevalence of food allergy has occurred over a short period of human evolution, implying that food allergy does not arise as a result of germline genetic changes alone. It therefore seems plausible that one or more environmental exposures can induce epigenetic changes that interrupt the default immunologic state of tolerance to foods.

There are however many studies to suggest that genetic factors play a role in the development of food allergy. For example, a family history of FA is itself a risk factor for FA. A child has a 7-fold increase in the risk of peanut allergy if there is a parent or sibling with PA.

The complex interplay between genetic and environmental factors giving rise to FA is perhaps best demonstrated by comparing concordance rates for allergy between genetically identical (monozygotic) and nonidentical (dizygotic) subjects.

Although previous twin studies have estimated a high degree of heritability for atopic diseases, such as asthma (87%) and AD (74%), a study by Sicherer et al. of 58 twin pairs estimated the heritability for PA to be as high as 82% to 87%. In a recent review, Hong et al. highlighted more than 10 genes (several involved in allergen presentation, a Th2-skewed immune system, or both) that have been associated with FA or food sensitization. However, genetically determined skin barrier dysfunction—associated with mutations in the gene encoding filaggrin (FLG)—has attracted the most interest, as this is known to predispose to multiple systemic atopic diseases.

The LEAP Study families represent an ideal opportunity to assess for genetic influences on peanut allergy in an atopic, well-phenotyped population. The mechanistic relevance of those assessments of various LEAP populations is that we would expect all study participants who develop peanut allergy to have filaggrin null mutations, or possibly mutations in other genes that encode for proteins that are important in skin barrier function. A variety of analysis approaches may be taken. Some of these are illustrated in a recent review of the influence of genetics on allergic outcomes.

#### 1.5 SUMMARY OF KNOWN AND POTENTIAL RISKS AND BENEFITS FOR PARTICIPANTS

The main risks of study participation relate to study assessments. These include venipuncture, skin prick testing and oral food challenge. Venipuncture is associated with a moderate risk of discomfort and a small risk of hematoma. Skin prick testing may be associated with localized swelling and redness.

Oral peanut food challenge in non-allergic subjects does not carry risk. In the subset of allergic individuals, risks associated with peanut challenges include nausea, vomiting, itching, urticaria, angioedema, asthma, other respiratory symptoms, and anaphylaxis, which can be life threatening.

In the study, DNA will be collected for genetic analyses. This is associated with a risk of loss of privacy.

## 2. OBJECTIVES

## 2.1 CO-PRIMARY OBJECTIVES

- 1. To assess whether early consumption of peanuts by high-risk infants results in a decreased risk of peanut allergy in children approximately 12 years of age.
- 2. To determine the prevalence of sensitization in younger siblings of LEAP participants who resided in the home at the time of the LEAP intervention, comparing younger siblings of LEAP participants who consumed peanut to younger siblings of LEAP participants who avoided peanut.

# 2.2 SECONDARY OBJECTIVES

## **LEAP Participants**

- To assess the effect of peanut consumption or avoidance in an at-risk study population (former LEAP participants) on additional allergic disease outcomes such as: a) allergic sensitization to select ingested allergens, b) allergic sensitization to select aeroallergens, c) reported type 1 immediate-onset food allergy, d) seasonal and perennial rhino-conjunctivitis, e) oral allergy syndrome, and f) asthma.
- 2. To assess the long-term safety of the LEAP intervention as determined by the frequency and severity of peanut-related adverse events as well as by nutritional evaluations.
- 3. To assess eczema severity by clinical assessment of SCORAD.
- 4. To define the long-term immunological impact of the intervention using cellular and humoral assessments of immune response related to the development of allergy or tolerance to specific allergens.

## LEAP Siblings

- 1. To assess the impact of environmental peanut exposure, derived from LEAP Food Frequency Questionnaires (FFQs) and peanut levels in bed dust at the LEAP 60 month visit, on prevalence of peanut sensitization and allergy in siblings of LEAP participants.
- 2. To control for allergen-specific effect of environmental exposure by assessing the prevalence of sensitization and reported food allergy to common food allergens including hen's egg white, cow's milk, sesame seed, and the five tree nuts assessed in the LEAP Study (Brazil nut, hazel nut, cashew, walnut, almond) in siblings of LEAP participants.
- 3. To assess the impact of peanut consumption in siblings during the first and second years of life on the development of peanut sensitization and allergy in these siblings of LEAP participants.
- 4. To characterize the allergy status in all siblings of LEAP participants.
- 5. To assess eczema severity by clinical assessment of SCORAD in siblings of LEAP participants.
- 6. To assess seasonal and perennial rhinoconjunctivitis, asthma, and eczema in the siblings of LEAP participants.
- 7. To assess safety as determined by the frequency and severity of peanut-related adverse events in the siblings of LEAP participants.

## **LEAP Parents**

- 1. To characterize the allergy status in all parents of LEAP participants.
- 2. To characterize environmental peanut exposure derived from peanut consumption questionnaires in all parents of LEAP participants.
- 3. To assess the prevalence of sensitization to common food and aeroallergens in all parents of LEAP participants.
- 4. To assess seasonal and perennial rhinoconjunctivitis, asthma, and eczema in all parents of LEAP participants.

# 2.3 EXPLORATORY OBJECTIVES

- 1. To assess skin barrier function by clinical assessment of Trans Epidermal Water Loss (TEWL) measurement in LEAP participants and siblings of LEAP participants.
- 2. To assess mechanistic correlates of allergy and tolerance, as described in section 7.
- 3. To collect genetic material for possible future research.
- 4. To characterize household peanut consumption and concentration of environmental peanut protein in dust.
- 5. To assess the impact of peanut consumption on dietary assessments derived from 3day food diaries in LEAP participants.
- 6. To summarize allergies to foods other than peanut.

# 3. STUDY DESIGN

# 3.1 DESCRIPTION

This is a long-term assessment of the LEAP randomized controlled study of early peanut consumption. LEAP participants are followed during an extended period of *ad-libitum* peanut consumption and then assessed for peanut allergy and other allergic outcomes at approximately age 12. In addition siblings and parents will be assigned to the intervention or control group based on the prior randomization of their LEAP participant sibling or child, respectively.

The flow of LEAP participants from screening through LEAP and LEAP-On is shown in Figure 1. The figure indicates how many individuals are likely to be available from various cohorts for enrollment into the study. In addition, siblings and parents of LEAP participants will be followed for allergic and genetic parameters.

## Figure 1. LEAP Screening, Participant, Sibling, and Parent Cohorts

The number of siblings in the Ad Lib section are based on findings in a survey regarding siblings of LEAP participants. These numbers represent an estimate of the total participants expected to enroll.

Participants in the current study derive from participants in previous LEAP trials and their families. The LEAP Screening Cohort has been described. The LEAP study enrolled 640 participants, of whom 556 were also studied in the LEAP-On follow up study. All participants who enrolled in LEAP, including those who were not part of the intent-to-treat (ITT) population, are eligible to enroll in this study. Parents and siblings of LEAP participants who meet other eligibility criteria described in sections 4.2 and 4.3 are eligible to enroll.

We reviewed the ages and dates of enrollment of participants in the LEAP trial. The times of enrollment and participation are shown in Figure 2. We assume the trial opens for enrollment in March 1, 2018. The last day for enrollment is August 31, 2022. The study was extended to accommodate for slowed enrollment due to the COVID-19 pandemic. As a result of the study extension, participants are predicted to be older than originally planned. This difference is not likely to significantly alter the study outcomes, as allergic status is unlikely to change during this time interval. These parameters allow us to describe expected ages at enrollment of LEAP participants in the current study.

Participant A, and similar participants who were relatively old at enrollment and enrolled relatively early in LEAP, could be as old as [10.9 months + (August 31, 2022 - February 2, 2007)] = 332 + 5689 days or 16.5 years.

For participant E, and similar participants who were relatively young at enrollment and enrolled relatively late in LEAP, the minimum age for eligibility applies (section 4.1.1). At the time of trial opening they would be as young as [4.5 months + (March 1, 2018 - March 20, 2009)] = 137 + 2844 days or 9.3 years. The minimum age of 9.5 years for eligibility means such participants could therefore be eligible for enrollment 0.2 years after March 1, 2018, or in May 2018 or after.

## 3.2 STUDY ENDPOINTS

## 3.2.1 Co-Primary Endpoints

#### **LEAP Participants**

The primary endpoint is the rate of peanut allergy in LEAP participants at 144 months of age. The strategy for determination of peanut allergy is outlined in section 3.3.

#### **LEAP Siblings**

The primary endpoint is the rate of peanut sensitization in younger siblings who resided in the home of the LEAP participant on or before LEAP Visit 60, as assessed in the current LEAP Trio study. The strategy for determination of peanut sensitization is outlined in section 3.3.2.

## 3.2.2 Secondary Endpoints

#### LEAP Participants, Siblings, and Parents: Clinical

- 1. Amount of peanut consumption as measured by peanut consumption questionnaires.
- 2. Skin-prick test wheal sizes to peanut, other select foods, and aeroallergens.
- 3. Specific-IgE measurements to peanut, other select foods, and aeroallergens.
- 4. Eczema severity by clinical assessment of SCORAD in LEAP participants and siblings.

- 5. Prevalence of asthma, rhinitis and eczema evaluated using a combination of questionnaires, examinations, and lung function testing in LEAP participants and siblings.
- 6. Prevalence of asthma, rhinitis and eczema evaluated using questionnaires in parents.
- 7. Prevalence of peanut allergy in LEAP siblings and parents.
- 8. Peanut-related adverse events in LEAP participants and siblings.

#### 3.2.3 Exploratory Endpoints

#### LEAP Participants, Siblings, and Parents

- 1. Prevalence of allergies (other than peanut).
- 2. Dietary assessment questionnaires in LEAP participants.
- 3. Transepidermal Water Loss (TEWL) in LEAP participants and siblings.
- 4. Household peanut consumption questionnaires and concentration of environmental peanut protein in dust collected from the participants' homes.

#### LEAP Participants, Siblings, and Parents: Mechanistic

Endpoints for mechanistic studies are described in section 7.

## 3.3 STUDY DEFINITIONS

#### 3.3.1 Determination of Primary Peanut Allergy

Peanut allergy status will be determined by peanut challenge where possible. Peanut challenges are described in section 6.7. Participants meeting criteria for peanut oral allergy syndrome in the absence of primary peanut allergy as described in section 3.3.5 will not be considered peanut allergic.

Individuals consuming at least 2g of peanut protein without reaction on at least one occasion in the last year will be considered peanut tolerant.

If oral challenge is not possible and participants do not meet the above criteria for tolerance, peanut allergy status will be determined by an internally and externally validated novel peanut allergy prediction model, the manuscript for which is currently in preparation: *Developing a Prediction Model for Determination of Peanut Allergy Status in The LEAP Trio Study*; Sever ML, Calatroni A, Du Toit G, et al. The model was developed using data from the LEAP participants, and incorporates peanut wheal size (mm), peanut specific IgE (kU/L), IgG4:IgE Ratio and Ara h2 (kU/L). The model performs with high level of accuracy, and continues to perform reasonably well in the context of missing blood or skin prick data. This model replaces the previously specified algorithm for determination of peanut allergy status. The details of the prior algorithm are included in the Appendix 2 for historical reference.

#### 3.3.2 Determination of Peanut Sensitization

Peanut sensitization is defined as:

- a) Sp-IgE  $\geq$  0.35kU/L or
- b) Sp-IgE to individual peanut component Ara  $h2 \ge 0.1 kU/L$  or
- c) Skin prick test to peanut  $\geq$  3mm.

## 3.3.3 Definition of Rhinoconjunctivitis

**Perennial rhinoconjunctivitis.** Sensitization to a perennial allergen and clinical history of rhinoconjunctivitis symptoms experienced when exposed to the relevant allergen.

**Seasonal rhinoconjunctivitis.** Sensitization to a seasonal allergen and clinical history of rhinoconjunctivitis symptoms experienced during the relevant season.

## 3.3.4 Definition of Asthma

Asthma will be diagnosed if one of the following three definitions is met:

- A history of cough, wheeze, or shortness of breath that meets all three of the following criteria: (1) was responsive to therapy with bronchodilators on two or more occasions in the previous 24 months, and (2) required one visit to a physician in the previous 24 months, and (3) occurred during the night, during early morning, or upon exercising in the intervals between exacerbations at any time in the previous 12 months, or
- Participant report of an asthma diagnosis on the Medical History CRF with current use of asthma medications (SABA or controller) on the Concomitant Medications CRF, or
- Participant report of transient wheeze on exposure to a suspected allergen with confirmatory allergy tests.

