When considering IgG4 and the ratio of peanut specific IgG4:IgE, they were both significantly higher in the peanut consumption group compared to the peanut avoidance group (p<0.001) at 60 months but also 72 months (after a yearlong period of avoidance (p<0.001)). These findings therefore favour those parameters traditionally associated with tolerance. However, in the consumption group, values of peanut IgG4 had started to decrease, even at 30 months of age (when peanut consumption was ongoing). The longer-term trajectory of IgG4, and clinical relevance thereof, will become apparent after the determination of peanut allergy at 12 years of age in the LEAP Participant cohort.

Many children with peanut allergy develop concomitant sensitization and allergy to other peanut-related foods such as tree nuts and sesame. This adds an additional burden both in terms of quality of life and morbidity associated with living with allergic disease. Similarly, early life eczema and egg allergy have been shown to be a risk for asthma, and possibly allergic rhino-conjunctivitis. We will assess the natural history of these conditions in an atopic population and will assess whether the benefits of the LEAP intervention extend to other atopic disease and other food allergens.

The nutritional consequences of consuming peanut in the LEAP Study has been published. The current study will help determine if these benefits are sustained beyond the first six years of life and after participants have been eating peanut *ad-libitum*.

We therefore aim to further investigate the clinical, immunological and nutritional safety findings of the LEAP and LEAP-On Studies. The findings will provide an opportunity to improve our understanding of how early-life introduction of peanuts may promote the development of tolerance at 12 years of age and will serve as an additional safety evaluation of this nutritional intervention.

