# 6.5 ALLERGY ASSESSMENTS

- SPT for peanut (see section 6.6)
- IgE total
- IgE and IgE component resolved diagnosis (CRD) for peanut
- IgG for peanut
- IgG4 and IgG4 component resolved diagnosis (CRD) for peanut
- Peanut oral food challenges
- SPT to ingested allergens by extract to include hen's egg white, tree nuts, sesame; fresh food to include hens egg white, and if milk and sesame equivocal on extract, fresh milk and tahini
- SPT to inhaled allergens by extract to include Timothy grass, birch pollen, alternaria mould, cat and dog dander, and dust mite (*Dermatophagoides pteronyssinus*)
- Sp-IgE to ingested allergens to include hen's egg white, cow's milk, peanut, sesame, Brazil nut, walnut, cashew and almond
- Sp-IgE to inhaled allergens to include dust mite, cat, dog, alternaria, Timothy grass and birch pollen

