8.3.7. Secondary Endpoint 5/6: Asthma prevalence

The asthma evaluation assessments, allergen test results, medical history and concomitant medications data will be used in all 4 cohorts (LEAP Participants, Older Siblings, Younger Siblings, and Parents) to determine which participants meet the protocol definition of asthma diagnosis provided in protocol section 3.3.4:

Asthma will be diagnosed if one of the following three definitions is met:

- A history of cough, wheeze, or shortness of breath that meets all three of the following criteria: (1) was responsive to therapy with bronchodilators on two or more occasions in the previous 24 months, and (2) required one visit to a physician in the previous 24 months, and (3) occurred during the night, during early morning, or upon exercising in the intervals between exacerbations at any time in the previous 12 months, or
- Participant report of an asthma diagnosis on the Medical History Case Report Form (CRF) with current use of asthma medications (Short-acting beta-agonist [SABA] or controller) on the Concomitant Medications CRF, or
- Participant report of transient wheeze on exposure to a suspected allergen with confirmatory allergy tests.

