8.3.7.1. LEAP Participants

The prevalence of asthma in the LEAP Participants in the ITT population will be compared between LEAP Consumers and LEAP Avoiders using a two-tailed, chi-squared test at the 0.05 level of significance.

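### Asthma criterion 3 is not limited to inhaled allergens, so wheeze in a peanut reaction can be counted as asthma and would bias the secondary asthma comparison in favour of consumers

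*Protocol*

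**What the plan says.** Protocol 3.3.4 states that "Asthma will be diagnosed if one of the following three definitions is met", so the third definition is sufficient alone. It reads "Participant report of transient wheeze on exposure to a suspected allergen with confirmatory allergy tests". It sets no allergen class, test threshold, look-back period or number of episodes; the first definition has 24- and 12-month windows.

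SAP 8.3.7 repeats the three definitions and gives the data sources: "The asthma evaluation assessments, allergen test results, medical history and concomitant medications data will be used in all 4 cohorts". The test results are not restricted to inhaled allergens. SAP 8.3.7.1 says asthma prevalence in LEAP participants will be "compared between LEAP Consumers and LEAP Avoiders using a two-tailed, chi-squared test at the 0.05 level of significance". SAP 8.3.7.2 applies the same definition to siblings and parents, with a random family effect.

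The comparison has a stated purpose. In Protocol 1.2 the investigators say they "will assess whether the benefits of the LEAP intervention extend to other atopic disease and other food allergens", and Protocol 2.2 names asthma among the secondary objectives for LEAP participants.

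**The concern.** A peanut reaction fits the wording. Protocol 1.5 says that in allergic individuals the "risks associated with peanut challenges include nausea, vomiting, itching, urticaria, angioedema, asthma, other respiratory symptoms, and anaphylaxis". Wheezing is a major criterion for a positive challenge in Protocol Table 1. The confirmatory test is available too, because Protocol 6.5 includes peanut skin-prick testing and "IgE and IgE component resolved diagnosis (CRD) for peanut".

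Misclassification unrelated to arm would mainly dilute an asthma difference. This kind scales with peanut allergy, the outcome that the intervention changes. If it occurs, part of the peanut effect is relabelled as an asthma effect, in the direction that Protocol 1.2 would read as a wider benefit. No planned analysis separates asthma cases by the definition they met or removes those that rest on a food reaction.

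The documents do name the allergen class elsewhere. Perennial rhinoconjunctivitis in Protocol 3.3.3 requires "Sensitization to a perennial allergen and clinical history of rhinoconjunctivitis symptoms experienced when exposed to the relevant allergen". SAP 8.3.8 adds sensitization thresholds, and SAP 8.4.4.1 and 10.1 treat aeroallergens as a separate group.

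**Working it through.** **Inputs from the documents.** Protocol 9.3 gives 311 avoiders and 319 consumers potentially eligible. At 80% enrolment this is 0.80 × 311 = 248.8 and 0.80 × 319 = 255.2, so 249 and 255. Peanut allergy rates (avoiders vs consumers) are 15% vs 6% in the planning example, 17.2% vs 3.2% at month 60 (both Protocol 9.3) and 18.6% vs 4.8% at month 72 (Protocol 1.1).

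**Inputs the documents do not give (assumed).** True asthma prevalence b, equal in both arms: 10-30%. Share f of peanut-allergic children who report wheeze on peanut exposure: 10-33%.

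**Step 1: reproduce the plan's power for peanut allergy.** This confirms the arm sizes and the test approximation; the plan states no power for asthma.
- Pooled rate = (249 × 0.15 + 255 × 0.06) / 504 = 0.1045.
- SE under no difference = √[0.1045 × 0.8955 × (1/249 + 1/255)] = 0.02725.
- SE under the alternative = √[0.15 × 0.85/249 + 0.06 × 0.94/255] = 0.02708.
- Power = Φ[(0.09 − 1.96 × 0.02725) / 0.02708] = Φ(1.351) = 91.2%, against 91% stated.
- With 70% enrolled (218 and 223) the same formula gives 87.2%, against about 87% stated.

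**Step 2: the false difference.** Let PA be the peanut allergy rate in an arm. If wheeze in a peanut reaction is independent of true asthma:
- observed asthma rate = b + (1 − b) × f × PA
- false difference = (1 − b) × f × (PA avoiders − PA consumers)

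At 15% vs 6%:
- smallest: 0.70 × 0.10 × 0.09 = 0.63 points
- middle: 0.80 × 0.20 × 0.09 = 1.44 points (22.40% vs 20.96%)
- largest: 0.90 × 0.33 × 0.09 = 2.67 points

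**Step 3: type I error of the planned two-sided test when there is no true asthma effect.** In the middle case SE = 0.0367 and the shift is 0.0144 / 0.0367 = 0.392. The rejection rate is Φ(0.392 − 1.96) + Φ(−0.392 − 1.96) = 6.8%. The same calculation across the range, with 249 and 255 children, gives:

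| True asthma b | f = 10% | f = 20% | f = 33% |
|---|---|---|---|
| 10% | 0.81 points, 6.0% | 1.62 points, 8.7% | 2.67 points, 14.4% |
| 20% | 0.72 points, 5.5% | 1.44 points, 6.8% | 2.38 points, 9.7% |
| 30% | 0.63 points, 5.3% | 1.26 points, 6.1% | 2.08 points, 7.9% |

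With f = 0 the rate is 5.0%.

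**Step 4: sensitivity to the inputs.**
- *Larger peanut gap.* At month-60 rates the same ranges of b and f give 1.0-4.2 points and 5.7-28.4%; the middle case is 2.2 points and 9.4%.
- *More overlap.* Suppose half of the wheezing children already meet criteria 1 or 2, so that 0.5 replaces (1 − b). At planning rates the worst corner becomes 0.5 × 0.33 × 0.09 = 1.5 points and 8.1%. At f = 20% the type I error is at most 6.2%, and at f = 10% at most 5.3%.

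**The case against.** The strongest reply is that the wording permits the leak but does not show that it happens. Protocol 6.3.1 records asthma symptoms, food reaction history and the food allergy questionnaire as separate items. SAP 8.3.7 does not list either food item among its asthma sources. A wheeze in a peanut reaction is therefore counted only if it also reached the asthma evaluation or the medical history, and those forms are not visible here. Protocol 9.2.4 limits relevant medical history to the past 12 months, which may exclude older reactions by that route. Wheeze seen by staff at the Visit 144 challenge is not clearly a participant report. All of this stands, and it makes the leak conditional.

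The size is also open to challenge. Both b and f are assumptions. Independence probably overstates the leak, because children who wheeze in reactions are more likely than average to have asthma already. Applying f to every allergic child presumes that each had a reaction to report, while allergic avoiders may have had little exposure. These points stand as well and pull the figures down.

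A reader might infer that every peanut-allergic child who has wheezed will be counted as asthmatic, or that the peanut effect alone will yield a significant asthma benefit. The documents support neither. The data route is uncertain. At planning rates, even the worst corner of the range leaves the test non-significant about 86% of the time (100% − 14.4%).

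The reply does not remove the gap in the definition: a reported wheeze after peanut with a positive peanut test meets the rule as written.

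**Conclusion.** The point holds as a conditional bias in one secondary endpoint. If wheeze in a food reaction reaches the asthma data, criterion 3 counts it. For peanut the error would favour consumers, because peanut allergy was more frequent in avoiders at months 60 and 72 and is planned to be so at month 144.

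At planning rates, and with the assumed 10-33% wheeze and 10-30% true asthma, the false difference is 0.6-2.7 points and the type I error 5.3-14.4%, about 6.8% mid-range. It is larger if the peanut gap stays near its month-60 size, and smaller if wheezing children already meet criteria 1-2 or allergic avoiders had no reaction to report. None of these sizes can be derived from the documents alone.

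Neither co-primary analysis is affected. In siblings and parents the direction would follow their own peanut-allergy difference. The change is worth making because it is cheap and protects a question the protocol sets out to answer.

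**What to change.** In SAP 8.3.7, with matching wording in Protocol 3.3.4, count criterion 3 only when the confirmatory test is to an inhaled allergen listed in Protocol 6.5 (dust mite, cat, dog, alternaria, Timothy grass, birch).

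Add a sensitivity analysis that excludes participants who qualify only through wheeze in an immediate food reaction, using the food reaction history collected under Protocol 6.3.1. It is needed as well as the restriction: a child who wheezed only after peanut may also be sensitized to an inhaled allergen, and the test result alone would not separate the two.

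**Cost.** No new data are needed. The asthma count falls slightly. Where the asthma form did not record the trigger, it must be taken from the food reaction history, and some cases may stay unclassified. If the sponsor regards this as a change to a principal feature of the plan, Protocol 9.5 requires an amendment with review.
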